3. OBJECTIVES

3.1. Study Objectives

3.1.1. Primary Objectives

- To establish the natural history of BK viremia in a multicenter population of renal and renal/pancreas transplant patients, to include incidence, time to onset, duration, and quantitation of viral load;
- To assess associations between BK viremia and decline in GFR in renal transplant recipients.

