4.1. Informed Consent and Enrollment

In an effort to capture subjects early in the course of the evolving BK infection and to avoid subjects who have already developed evidence of BKV-induced nephropathy (BKVN), this protocol will emphasize the natural history of early-onset BK viremia. Obtaining informed consent early in the peri-transplant period is encouraged, although enrollment and study-related specimen collections will not begin until ≥ 4 weeks post-transplant. The consent form will secure the subject's informed consent to participate in the screening phase as well as the intensive monitoring phase (if qualifying viremia is subsequently identified).

Consented subjects can be enrolled as early as 4 weeks and as late as 100 days following renal/renal-pancreas transplant surgery. The 4-week delay prior to enrollment and initiation of specimen collection will allow post-transplantation stabilization of renal function, immunosuppressive dosing, and other clinical parameters.

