4.2. Prospective Screening Phase

Approximately 450 subjects will be screened for BK viremia (15% over-enrollment allowed, to a maximum of 518 screened subjects). During the screening phase, subjects will submit blood (plasma) for quantitative measurement of BKV DNA approximately every 4 weeks, ± 7 days, for 6 months (timed from the date of transplantation) and then approximately every 8 weeks, ± 14 days for 6 months. Also, urine specimens will be collected at each visit and stored for subsequent testing. During the screening phase, the specified intervals between sample collections should be followed as closely as possible, but may vary with subject availability. If qualifying BK viremia is not detected, surveillance will terminate approximately 12 months after the date of transplantation (or when another study termination endpoint is reached, whichever occurs sooner).

NOTE: BKV PCR results of $\geq 10,000$ from the study central laboratory, the site laboratory, or a reference laboratory are acceptable to qualify the patient for inclusion in the Intensive Monitoring Phase of the study.

NOTE: Non-study patients who are determined to have a qualifying blood BK viral load ($\geq 10,000$ copies/ml) during the course of routine clinical care (i.e., patients not consented and not identified by prospective screening/surveillance) will also be eligible for enrollment directly into the intensive monitoring surveillance phase after providing consent as long as they remain within the window of ≤ 100 days following transplantation.

Subjects will remain in the screening/surveillance phase: 1) for 12 months post-transplantation; 2) until qualifying BK viremia is documented; 3) until renal graft failure, re-transplantation, and/or initiation of chronic dialysis occurs; 4) death; 5) until subject decides to terminate participation; 6) until the investigator decides that the subject should terminate participation; or 7) until the study closes (whichever occurs first). Reason for termination of participation in the study will be documented.

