5.3.2. Exclusion Criteria

- Evidence of proven or suspected BKVN by clinical or pathologic diagnostic criteria;
- Initiation of chronic dialysis post-transplantation due to graft failure.

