8. STATISTICAL CONSIDERATIONS

8.1. Study Hypothesis

Elucidation of the natural history of BK viremia in renal transplant patients will identify those groups at high risk for developing BKVN who may potentially benefit from therapeutic interventions (when these become available). In particular, it is of interest to compare the change in the glomerular filtration rate (GFR) a year after transplant between the BKV viremic and non-viremic subjects. We hypothesize that BKV viremia will have a negative effect on renal function as measured by GFR.

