We are also interested in comparing the change in GFR between those with and without BKV viremia. In this power analysis, we will only be concerned about the change from baseline (time of enrollment) to Month 12 (time post-transplant). Assuming the standard deviation of the change in GFR is assumed to be the same for those with and without BKV viremia and equals 10.9 ml/min/1.73 m² (Ref: Srinivas TR, Flechner SM, Poggio ED, et al. Glomerular filtration rate slopes have significantly improved among renal transplants in the United States. Transplantation 2010; 90:1499-505.). With 40 BKV viremia subjects and 410 non-BKV viremia subjects, we will detect a mean difference in the change in GFR of at least 5.9 ml/min/1.73 m² with 90% power between these two groups of subjects at 5% level of significance based on a t-test. In the final analysis, we will be using all available GFR data for each subject which should increase the power as more information is used. This will enable us to still use data from subjects who dropped out before the end of the study.

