8.4.1. Primary Outcome Analysis

Incidence of BK viremia will be estimated using a 95% confidence interval for single proportion. Logistic regression will be used to investigate the risk factors for BKV viremia and BKVN. Factors will include:

- Donor-derived factors:
 1. Deceased donor – Standard criteria donor (SCD), Donor after cardiac death (DCD), Expanded criteria donor (ECD)
 2. Living donor – related donor or unrelated donor
 3. ABO incompatibility
 4. Total HLA mismatches
 5. HLA C7 status
 6. Race/ethnicity
 7. Sex
- Recipient-derived factors:
 1. Delayed graft function (DGF), defined as use of dialysis within 7 days of the transplant
 2. Cold ischemia time (CIT)
 3. Warm ischemia time (WIT)
 4. Use of stents
 5. HLA C7 status
 6. Type/intensity of immunosuppression, including corticosteroids
 7. Acute rejection
 8. Age
 9. Race/ethnicity
 10. Sex

To compare the change in GFR over time between those with and without BKV viremia, we use all available GFR data from each subject. We will use mixed model for repeated measures to analyze the GFR data over time. This analysis method will allow us to use any of the available GFR data

even if they are not complete. We will determine the appropriate covariance structure to use as indicated by the Akaike Information Criterion.

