8.4.2. Secondary Endpoints

The distribution of the time to onset and duration of BKV viremia will be estimated using survival analysis methods such as Kaplan-Meier estimator for a single group. This will provide estimates of the median time to onset or median duration of BKV viremia. To compare different groups and/or determine risk factors, we will use Cox proportional hazard regression model if the proportional hazards assumption is found to be reasonable. Otherwise, we will consider using parametric survival regression models (in particular, accelerated failure time model). Parametric regression models are useful especially in cases where sample sizes are small or when the percent censored is high. This will also be the tool of preference if there will be left-censored subjects, i.e., subjects who at enrollment show evidence of BK viremia. Cox model cannot handle left-censored data.

As with the BKV viremia, incidence of BKVN will be estimated using a 95% confidence interval for single proportion. We will utilize logistic regression to compare groups, or adjust for covariates or determine risk factor.

To investigate the change in the quantitative BK viremia over time and how it is associated with important factors such as the use of immunosuppressive therapy and recipient's demographic and clinical characteristics, we will again use mixed regression modeling for repeated measures.

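### The GFR comparison in section 8.4.1 names no covariates and no handling of subjects already viremic at enrolment, so run as written it gives a crude contrast

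*Combined protocol and SAP*

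**What the plan says.** The second primary objective (3.1.1) is "To assess associations between BK viremia and decline in GFR in renal transplant recipients". Section 8.1 wants to "compare the change in the glomerular filtration rate (GFR) a year after transplant between the BKV viremic and non-viremic subjects" and hypothesises a negative effect of viremia. Section 8.2.1 bases power on "the change from baseline (time of enrollment) to Month 12 (time post-transplant").

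For the analysis "To compare the change in GFR over time between those with and without BKV viremia", section 8.4.1 gives a mixed model for repeated measures, all available GFR data and AIC selection of the covariance. The donor and recipient factors in that section belong to the logistic regressions for viremia and BKVN. Section 8.4.2 plans covariates for BKVN incidence and for viral load over time, but does not mention GFR.

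Viremic patients can enter the study in two ways:

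- Section 4.1 states "Consented subjects can be enrolled as early as 4 weeks and as late as 100 days" after surgery. The related exclusion in 5.3.2 is "Evidence of proven or suspected BKVN by clinical or pathologic diagnostic criteria", which does not cover viremia alone.
- Under 4.2, non-study patients with a qualifying viral load found in routine care "will also be eligible for enrollment directly into the intensive monitoring surveillance phase".

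Section 8.4.2 foresees "subjects who at enrollment show evidence of BK viremia", but only in choosing a survival model.

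**The concern.** Viremic and non-viremic subjects are not randomised groups. The plan itself treats donor type, delayed graft function and cold ischemia time as possible risk factors for viremia. If such a factor also changes the course of GFR, a crude contrast attributes its influence to viremia, or lets it mask a real association.

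The baseline raises a second problem. It is the enrolment GFR, taken between 4 weeks and 100 days after transplant. In a subject already viremic by then, any earlier loss is absorbed into the baseline and the later change looks smaller.

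At stake is the analysis behind the second primary objective and the only comparison named in 8.1. If covariates and the handling of entry viremia stay open, they could also be chosen after results are seen.

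**Working it through.** **1. The plan's own figure.** Inputs from 8.2.1 are 40 viremic and 410 non-viremic subjects, SD 10.9, 5% level, 90% power and a t-test. SE = 10.9 × √(1/40 + 1/410) = 1.81. The noncentral t (448 df, two-sided) gives a detectable difference of 5.87 and 90.3% power at 5.9. The stated 5.9 reproduces.

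**2. Confounding (all inputs assumed).** Shift = difference in factor prevalence × the factor's effect on GFR change. Take one factor 10 to 30 percentage points more common in viremic subjects and worth 3 to 6 mL/min/1.73 m².

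- Smallest shift: 0.10 × 3 = 0.3, or 5% of 5.9.
- Largest shift: 0.30 × 6 = 1.8, or 31% of 5.9.
- With no true difference, the two-sided 5% test then rejects in 5.3% (shift 0.3), 6.3% (0.6), 10.2% (1.2) or 16.9% (1.8) of studies.

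The shift could equally run the other way and hide an association.

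**3. Viremic at entry (assumed onset pattern).** Let enrolment be uniform over days 28 to 100, that is, months 0.92 to 3.29. Let 60, 75 or 90% of onsets be uniform over Months 1 to 6, and the rest later.

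- An early-onset subject is viremic before enrolment with probability [(3.29 − 1)² / 2] / (3.29 − 0.92) / 5 ≈ 0.22.
- Multiplying by 0.60, 0.75 and 0.90 gives about 13, 17 and 20% of viremic subjects, or 5 to 8 of 40.
- Their mean time from onset to enrolment is (3.29 − 1) / 3 ≈ 0.76 month.
- The share of loss before enrolment is about 0.76 / 2 = 38% if the loss is complete in 2 months. By simulation it is 7% if the loss is linear to Month 12.
- Dilution of the contrast runs from 0.13 × 0.07 ≈ 1% to 0.20 × 0.38 ≈ 8%. A true 5.9 would appear as 5.84 to 5.43, with power of 90 to 85% for 40 against 410.

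Onset before Month 1 would raise these values. If direct enrollees brought the class to 20 of 40, dilution would be 0.5 × 0.07 ≈ 4% to 0.5 × 0.38 = 19%, with power of 88 to 75%.

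**4. Cost of excluding these subjects.** The same t-test inputs with fewer viremic subjects give:

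| Viremic subjects | Detectable difference | Power at 5.9 |
|---|---|---|
| 40 | 5.87 | 90.3% |
| 35 | 6.24 | 86.6% |
| 32 | 6.50 | 83.7% |
| 20 | 8.11 | 65.5% |

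Exclusion therefore costs about as much power as the dilution it removes, or more.

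**5. Cost of adjustment.** Adjusted SD = 10.9 × √[(1 − R²y)/(1 − R²x)]. R²y is the share of variance in GFR change explained by the covariates, and R²x their squared correlation with viremia. With both between 0 and 0.2 (assumed) and 40 against 410, the detectable difference runs from 5.25 to 6.56 and power at 5.9 from 95 to 83%. If the two are equal, nothing changes.

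**The case against.** The strongest reply is that 8.4.1 is brief rather than wrong. A reader might infer that the plan specifies an unadjusted model and deliberately pools subjects viremic at entry. It states neither; both are read from silence. Section 8.4.2 uses mixed modelling with demographic and clinical factors for viral load, so adjustment is not foreign to the plan. The objective asks for associations, which a crude contrast can describe. GFR change appears in none of the endpoint lists in 3.2, and every bias size above is assumed.

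Much of this stands. It limits the point to what the analysis would deliver if run as written, and it limits any claim about magnitude. It does not remove the point. The section sets out the method for a primary objective whose hypothesis is worded as an effect, and the factors needed for a better contrast are already collected.

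A reader might also infer that subjects viremic at entry should be left out of the main analysis. The documents do not support that. Section 4.1 emphasises early-onset viremia, so exclusion would remove the earliest cases, and step 4 shows that it gains no power. Nor do the documents show that direct enrollees will be numerous, since 8.2.1 sizes the study on viremia arising in the screening group.

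**Conclusion.** The point holds as a gap in the specified model. Run as written, the comparison cannot separate viremia from recorded donor and graft factors, and loss before enrolment is counted as baseline. Confounding is the stronger ground: 0.3 to 1.8 mL/min/1.73 m² for one assumed factor, with unknown direction. The entry-viremia part is probably small, about 1 to 8% under the assumed onset patterns.

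A reader might take this to mean that 5.9 is miscalculated or that the result will be biased by a known amount. Neither follows. The figure reproduces, and the documents give neither the strength of any confounder nor the share of subjects viremic at entry. The change should be made before the data are analysed.

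**What to change.** In 8.4.1:

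- **Main analysis.** Keep all viremic and non-viremic subjects. Keep change in GFR from enrolment to Month 12 after transplant as the contrast, through a group-by-time term. Treat the enrolment GFR as baseline only, because enrolment can fall in Months 1 to 3 and the value must not also count as a response. Place later GFR values on the Appendix A-1 months, with a stated rule for the extra readings under Appendix A-2.
- **Adjustment.** Use factors fixed before enrolment and recorded under 6.1: donor type, donor age, delayed graft function, cold ischemia time, recipient age, sex and race/ethnicity, with factor-by-time terms. Do not adjust for immunosuppression changes made after viremia, which 7.4 allows as a response to it.
- **Sensitivity 1.** Fit the same model without direct enrollees and subjects with a qualifying PCR at or before the enrolment draw. Repeat it excluding any detectable viremia at enrolment.
- **Sensitivity 2.** Fit the main model additionally conditioned on enrolment GFR. Keep this separate, because in non-randomised groups conditioning can give a different answer from the change contrast in 8.2.1.
- **Reporting.** Give the number of viremic subjects with a Month-12 GFR, since 4.4 ends follow-up six months after resolution. Give the number dropped for missing covariates. Describe the result as an association.

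The cost is SAP wording and modest programming. Subjects missing a covariate drop out, because 8.4 rules out imputation, and the interval may widen slightly if covariates correlate with viremia. The exclusion analysis has lower power (about 84 to 87% at 5.9 if 5 to 8 of 40 are removed, 65% if 20 are), so it belongs among the sensitivity analyses.

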8.4.2. Secondary Endpoints

The distribution of the time to onset and duration of BKV viremia will be estimated using survival analysis methods such as Kaplan-Meier estimator for a single group. This will provide estimates of the median time to onset or median duration of BKV viremia. To compare different groups and/or determine risk factors, we will use Cox proportional hazard regression model if the proportional hazards assumption is found to be reasonable. Otherwise, we will consider using parametric survival regression models (in particular, accelerated failure time model). Parametric regression models are useful especially in cases where sample sizes are small or when the percent censored is high. This will also be the tool of preference if there will be left-censored subjects, i.e., subjects who at enrollment show evidence of BK viremia. Cox model cannot handle left-censored data.

As with the BKV viremia, incidence of BKVN will be estimated using a 95% confidence interval for single proportion. We will utilize logistic regression to compare groups, or adjust for covariates or determine risk factor.

To investigate the change in the quantitative BK viremia over time and how it is associated with important factors such as the use of immunosuppressive therapy and recipient's demographic and clinical characteristics, we will again use mixed regression modeling for repeated measures.

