3.2.2. Secondary endpoints

- Timing of onset of BK viremia (number of days post-transplant)

- Duration of BK viremia
- Incidence of BKVN in the study population
- Dynamics of quantitative measurements of BK viremia over time
- Frequency of donor and recipient-related risk factors for BV viremia, including:
 - a. Donor-derived factors:
 - i. Deceased donor – Standard criteria donor (SCD), Donor after cardiac death (DCD), Expanded criteria donor (ECD)
 - ii. Living donor – related donor or unrelated donor
 - iii. ABO incompatibility
 - iv. Total HLA mismatches
 - v. HLA C7 status
 - vi. Race/ethnicity
 - vii. Sex
 - b. Recipient-derived factors:
 - i. Delayed graft function (DGF), defined as use of dialysis within 7 days of the transplant
 - ii. Cold ischemia time (CIT)
 - iii. Warm ischemia time (WIT)
 - iv. Use of stents
 - v. HLA C7 status
 - vi. Type/intensity of immunosuppression, including corticosteroids
 - vii. Acute rejection
 - viii. Age
 - ix. Race/ethnicity
 - x. Sex
- Frequency of clinical outcomes that are potentially related to BKV infection, including:
 - a. subject death,
 - b. loss of graft function as defined by GFR <10 mL/min/1.73 m²
 - c. development of urinary outlet obstruction
 - d. development of gross hematuria
 - e. development of lymphocele
 - f. acute rejection
 - g. initiation of dialysis
 - h. re-transplantation
 - i. renal biopsies

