4. STUDY DESIGN

The primary objective is to define the natural history of BK viremia in renal or renal-pancreas transplant recipients. In order to understand the natural history of infection, we will measure the time to the development of BK viremia and its correlation with progression to end-organ disease (BKVN or BK hemorrhagic cystitis). Data from this intensive natural history monitoring period will allow for the identification of the types of high-risk patients who might benefit from future studies of therapeutic interventions for BKV infection, when effective therapy becomes available. This will be accomplished by serial quantitative BK DNA measurements by PCR in blood (plasma). It is anticipated that most samples (blood and urine) will be collected during routine standard-of-care clinic visits and will not require extra study visits. Phases of the study can be summarized as follows:

- Subject identification and informed consent. Informed consent should be obtained in the peri-transplant period (between 7 days pre-transplantation [T-7d] and 100 days post-transplantation [T+100 d]).
- Prospective screening for BK viremia. Enrollment and initiation of specimen collection should begin no sooner than 4 weeks after transplantation. Enrollment cannot occur later than 100 days after transplantation. **Subjects will be screened (collection of blood and urine for laboratory studies, including BK PCR) approximately monthly for 6 months (timed from the date of transplantation), then every other month for 6 months. For subjects who remain BKV-negative, screening will terminate approximately 12 months from the date of transplantation.**
- Intensive sampling of subjects identified with BK viremia. Subjects identified with qualifying viremia will be sampled approximately every two weeks until resolution of viremia (defined as PCR negative, or <1000 copies).
Note: Patients who did not participate in the prospective screening phase but are identified with BK viremia by standard-of-care testing may be enrolled, as long as they are still within 90 days of transplantation.
- Post-viremia follow-up. Following resolution of viremia, subjects will be sampled (collection of blood and urine) approximately monthly for 6 months (unless another termination event occurs sooner).

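### Onset of BK viremia is left- and interval-censored, but Section 8.4.2 plans an ordinary Kaplan-Meier curve and recognises left-censoring only in the regression

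*Combined protocol and SAP*

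**What the plan says.** Section 3.2.2 sets the time scale: "Timing of onset of BK viremia (number of days post-transplant". Section 4 sets the start of sampling: "Enrollment and initiation of specimen collection should begin no sooner than 4 weeks after transplantation". Section 4.1 gives the entry window: "Consented subjects can be enrolled as early as 4 weeks and as late as 100 days following renal/renal-pancreas transplant surgery". Section 4.2 then schedules samples about every 4 weeks to month 6 after transplant and about every 8 weeks to month 12. It also lets patients already found viremic in routine care enrol directly into intensive monitoring.

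For the analysis, Section 8.4.2 says: "The distribution of the time to onset and duration of BKV viremia will be estimated using survival analysis methods such as Kaplan-Meier estimator". This is for a single group, with a median. For regression, "we will use Cox proportional hazard regression model if the proportional hazards assumption is found to be reasonable"; otherwise a parametric survival model is considered. Of the parametric model it says: "This will also be the tool of preference if there will be left-censored subjects, i.e., subjects who at enrollment show evidence of BK viremia", and it adds: "Cox model cannot handle left-censored data". It gives no rule for how the Kaplan-Meier curve treats subjects viremic at entry, and none for onsets that fall between two samples.

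**The concern.** The clock starts at transplant, but study sampling starts 28 to 100 days later. A Kaplan-Meier curve run from day 0 on first-positive dates treats the unsampled period as event-free time. It dates a viremia that began before entry to the enrolment sample, and a later one to the visit that found it. The left-censoring provision does not reach the curve, which is the main descriptive output for onset.

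Time to onset is part of the first primary objective (Section 3.1.1), and Section 4.1 puts the emphasis on early-onset viremia. The early part of the curve is the part most affected. The date of first detection would then be read as the date of onset.

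**Working it through.** **1. The plan's own figure.** The documents give no figure for the onset analysis. The nearest is the event count in Section 8.2.1: at least 90% probability of 40 or more viremic subjects among 450 if the true rate is 11%. The exact binomial tail is P(X ≥ 40 | 450, 0.11) = 0.938, so it reproduces.

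**2. Who is under observation.** The window of days 28–100 is from Section 4.1; uniform entry within it is an assumption. The fraction enrolled by day t is (t − 28)/72:
- day 45: 17/72 = 24%
- day 60: 32/72 = 44%
- day 75: 47/72 = 65%
- day 90: 62/72 = 86%

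**3. Simulation A: prospectively screened subjects on the protocol's visits.** The entry window, the visit spacing and the BKVN exclusion ("Evidence of proven or suspected BKVN by clinical or pathologic diagnostic criteria") come from the documents. The rest is assumed:
- uniform entry;
- 12% viremic within a year, with onset gamma (shape 3, scale 45 days) truncated at 365 days, median day 119;
- exponential duration with median 60 or 120 days;
- 10% of those viremic at entry lost to the BKVN exclusion.

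With no drop-out before month 12, the Kaplan-Meier estimate at t is the number with a first positive sample by t, divided by N.

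| Cumulative onset | Day 60 | Day 90 | Day 100 | Month 12 |
|---|---|---|---|---|
| True | 1.8% | 3.9% | 4.7% | 12.0% |
| Kaplan-Meier from transplant | 0.4% | 2.0–2.1% | 2.9–3.1% | 9.5–10.4% |
| Delayed-entry Kaplan-Meier, viremic at entry dropped | 0.2% | 1.4% | 1.8–2.0% | 8.7–9.5% |
| Interval-censored, viremic at entry left-censored | 0.8% | 2.2–2.5% | 4.0–4.3% | as Kaplan-Meier |

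Repeat runs of one million subjects agreed within 0.2 points. The interval-censored row was solved on a weekly grid. A daily grid gave 1.4–1.5% and 3.0–3.4% at days 60 and 90, so the tabulated early values are the cautious ones.

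Per 450 subjects, by day 60 the ordinary curve shows 450 × 0.004 = 1.8 onsets against a true 450 × 0.018 = 8.1. By day 90 it shows 9.0–9.5 against 17.6.

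**4. Simulation B: adding direct enrollees.** Assumed: 11% viremic by month 12, onset from day 14, 75% of onsets by day 180, mean duration 120 days, uniform entry.

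| Ordinary Kaplan-Meier | Day 60 | Day 100 | Month 12 |
|---|---|---|---|
| True | 2.3% | 4.3% | 11.0% |
| No direct enrollees | 0.6% | 3.0% | 9.2% |
| 10 per 450 | 1.8% | 5.1% | 11.3% |
| 20 per 450 | 2.9% | 7.1% | 13.1% |

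Ten direct enrollees reverse the sign at day 100. Twenty reverse it at day 60 as well.

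**5. Cox model, true hazard ratio 1, onset assumptions as in B (standard error about 0.05 per run).** With equal entry times and subjects viremic at entry kept, the estimate is 1.01. With one group entering at days 28–45 and the other at days 60–100, it is 0.88–0.93 when those subjects are kept or partly lost, and 0.75 when all are lost. A control run with equal entry times and all of them lost gave 1.11, where no bias is expected. Shifts near 0.1 are therefore at the limit of what these runs can resolve.

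**The case against.** A reader might infer that the problem is left truncation affecting every screened subject, and that delayed-entry risk sets would repair it. The documents do not support that. Truncation requires that subjects enter only if event-free, but viremia does not bar entry. Section 5.3.2 excludes only BKVN and chronic dialysis, and Section 4.2 admits patients known to be viremic. Truncation is confined to patients who never enrol, for example because of BKVN, dialysis or death. On the protocol's own visits, delayed-entry Kaplan-Meier is further from the truth than the ordinary curve at every time tabulated. It drops the subjects viremic at entry and adds risk time before the next visit, when no event can be recorded.

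A reader might also infer that early onset is always understated, or that hazard ratios are biased in general. Step 4 shows that the direction depends on how many direct enrollees enter the curve, and the documents do not say. Step 5 shows that bias needs entry times that differ by factor. With about 40 events, the 95% limits for a balanced factor are already exp(1.96 × 2/√40) = 1.9-fold either way.

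Other objections stand in part:
- The primary endpoint is incidence, analysed as a proportion (Sections 3.2.1 and 8.4.1); timing of onset is a secondary endpoint.
- With about 12% incidence, the median onset named in Section 8.4.2 is not reached in the whole cohort under any of these methods.
- The 95% half-width at month 12 is 1.96 × √(0.12 × 0.88/450) = 3.0 points, so the month-12 gap is within sampling error.
- Routine-care PCR may find some viremia before enrolment.

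These points limit the importance of the defect. They do not supply the missing rule for the curve.

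**Conclusion.** The point holds as one of left- and interval-censoring. The plan sees left-censoring in the regression but leaves the onset curve on a method that cannot accommodate it, and it does not address interval-censoring at all. Among prospectively screened subjects, the ordinary curve shows under a quarter of true onset by day 60 (0.4% of 1.8%) and about half by day 90 (2.0–2.1% of 3.9%). Part of that gap comes from the visit interval rather than from late entry.

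These sizes rest on assumed onset, duration and entry distributions that the documents do not give, and the sign can reverse if direct enrollees are included. The interval-censored estimator was closer to the truth early on and no worse at month 12, but it does not recover everything. Viremia that cleared before entry or between visits is missed by any method, and the shape of the curve before day 28 cannot be learned from study samples. This should be changed in the analysis plan; it does not call the design or the primary incidence estimate into question.

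**What to change.** In Section 8.4.2:

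- Restrict the onset analysis to prospectively screened subjects. Report direct enrollees separately, and report the prevalence of viremia at enrolment.
- Replace the Kaplan-Meier curve for onset with an interval-censored estimator (Turnbull, or a parametric model) with transplant as origin. Subjects viremic at entry have onset between transplant and the enrolment sample; later onsets lie between the last negative and first positive samples.
- Use the same interval-censored likelihood for the onset regression.
- Describe the estimate as conditional on being free of BKVN and chronic dialysis at entry, and note that viremia cleared before entry or between visits is missed.
- Keep delayed-entry risk sets, if used at all, as a sensitivity analysis.
- Reconcile the limit for direct enrolment, which is 90 days in Section 4 but 100 days in the Protocol Summary and Section 4.2, so that the separately reported group is defined.

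No new data are needed, because the sample dates are already collected. The cost is SAP wording, modest code and wider intervals early in follow-up. In 300 simulated trials of 450 under simulation A, the standard deviation of the interval-censored estimate was about 0.8 points at day 60 and 1.0 at day 90, against 0.3 and 0.7–0.8 for the ordinary curve.
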